3.4 Vulnerable Populations

Children, fetuses, neonates, or prisoners are not included in this research study.

[figure not shown]
4. STUDY DESIGN**4.1 Preliminary Studies**

We have conducted two prior studies that inform the design of this trial. In the first, we evaluated the impact of plasma-based molecular testing in addition to tissue testing on the detection of actionable mutations in patients with metastatic NSCLC. In 229 patients who underwent concurrent plasma and tissue molecular testing, tissue alone detected targetable mutations in 21% of patients, whereas addition of plasma testing increased targetable mutation detection to 36%.¹³ Thus, plasma-based testing increased the rate of detection of therapeutically targetable alterations in metastatic NSCLC when used concurrently with tissue testing. In a second study, initiation of plasma-based testing performed at time of biopsy resulted in earlier availability of molecular results that translated into treatment recommendations in 75% of patients at initial oncology evaluation, compared to a baseline treatment recommendation rate of 47% in a historical control population.¹⁴ It also decreased time to guideline-concordant treatment initiation. However, implementing this intervention at the time of biopsy also resulted in over-testing of some patients (as tissue confirmation and stage were not yet established). The proposed pilot project will examine effectiveness of telehealth nurse navigation with an early comprehensive molecular testing blood draw during the periprocedural period associated with the patient's diagnostic biopsy in order to reach a larger proportion of patients, reduce disparities in molecular testing, and target testing more optimally.

4.2 Overview

Prior to the trial launch, we will use a rapid-cycle approach (RCA) to optimize delivery of the enhanced synchronous telehealth nurse navigation visit and coordination/default ordering of molecular testing. RCA procedures will involve design meetings with the study team, discussions with administrators and clinicians who are members of our Implementation Lab, as well as contextual inquiry with clinicians and patients to elicit feedback.

Objective 1: As shown in **Figure 1**, this two-arm pilot trial will randomize patients with suspected locally advanced/metastatic NSCLC who are scheduled for an appointment in the lung cancer evaluation clinic. Eligible patients will be identified by screening of clinical schedules by study staff using the EMR. Prior to or soon after completing an appointment in the lung cancer evaluation clinic, eligible patients will be randomized to either enhanced synchronous telehealth nurse navigation or to usual care nurse navigation.

Usual Care Arm:

Currently, in the standard care pathway at Penn Medicine, a patient who is being evaluated for lung cancer has an appointment within the lung cancer evaluation clinic and is then scheduled for a biopsy (e.g., bronchoscopy, transthoracic needle biopsy). After the biopsy is complete, the patient's clinician contacts the trained lung cancer nurse navigator, who then calls the patient to 1) review the roles of clinicians on the medical oncology care team; 2) provide brief education on lung cancer; and 3) review the patient's diagnostic history and coordinate collection or completion of imaging required for guideline-recommended cancer staging. In the standard care pathway at Penn Medicine this phone call between the patient and the lung cancer nurse navigator usually takes place after the biopsy is complete, though there are some cases in which the clinician asks the lung cancer nurse navigator to reach out to the patient sooner.

For patients randomized to the usual care arm of this study, the researchers will ask the clinicians and the lung cancer nurse navigator not to arrange plasma-based testing earlier than the date of the initial in-person medical oncology visit. Instead, the lung cancer nurse navigator can have the patient complete a blood draw for plasma-based testing on the same day as their initial in-person medical oncology visit.

Intervention (Telehealth) Arm:

Patients in the intervention arm will be scheduled for an enhanced synchronous telehealth visit with a trained lung cancer nurse navigator prior to tissue biopsy. The enhanced synchronous telehealth visit will ideally occur between the initial clinical appointment and diagnostic biopsy (typically a period between two and seven days). In addition to the activities conducted as part of usual care, the nurse navigator will: 1) provide more detailed and individualized education on lung cancer and the rationale for comprehensive molecular testing, including plasma-based tests; and 2) if the patient agrees to testing, pend a default order for plasma-based molecular testing (if not already ordered) for the clinician to sign and arrange for phlebotomy to be performed during the periprocedural window associated with the patient's tissue biopsy.

Objective 2: Using rigorous approaches proven successful in our prior work,^{15,16} we will recruit 20-30 patient participants of the primary trial and 10-15 clinicians and clinical leaders to complete semi-structured interviews following the active trial period.

Patients: We will oversample for Black patients to understand effectiveness by race/ethnicity and stratify by trial outcome and study arm to understand factors contributing to both success and failure (e.g., primary endpoint) in either group (5-10 patient in each stratum). Trial participants will be invited in randomly selected batches each month (to enhance capture over time) until we reach our target sample of approximately 20-30 patients. Patients will be invited to participate in interviews via email and/or letter within 6 weeks of their in-person oncology visit.

Clinicians: Recruitment for clinicians will be similar to the procedure for patients, except we will wait until the completion of the full trial to conduct interviews to avoid potential contamination. Clinicians will be purposively sampled by clinical role (e.g., oncologists, nurses, clinical leads) to enhance variation and invited via email. Recruitment will continue until we reach our target sample of 10-15 clinicians.

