Interventions	Eligible patients will be individually randomized to one of two arms: 
 1. Usual care – standard nurse navigation. 2. Enhanced nurse navigation – synchronous telehealth nurse navigation visit prior to biopsy.
Outcomes	
Objective 1: Receipt of a molecularly-informed treatment recommendation for patients with metastatic NSq NSCLC at the time of the patient's initial oncology visit.
 
Secondary Outcomes:
 
 1. Rate of telehealth visit completion 2. Rate of completion of comprehensive molecular testing (tissue and/or plasma testing) prior to initiation of first line therapy 3. Identification of one or more targetable mutations 4. Timeliness of molecularly-informed treatment recommendation 5. Overall survival 6. Intervention costs 7. Proportion of patients with diagnosis other than metastatic nonsquamous NSCLC (Telehealth arm only) 8. Time to treatment initiation 
Objective 2: Individual and contextual factors (e.g., treatment knowledge, medical mistrust, clinical beliefs, organizational climate, patient-centered communication, financial toxicity, and knowledge of genetic testing) shaping trial effectiveness and patient experience.

Primary Analysis	
Objective 1: Intention-to-treat (ITT) analyses for effectiveness using logistic regression.
 
Objective 2: Mixed methods evaluation of descriptive survey data and thematically coded interview data.

Study Oversight	[name] (PI) will be responsible for monitoring the trial and ensuring subject safety, as well as the integrity of the interventions and the data collected. Trial oversight will be conducted by the University of Pennsylvania Institutional Review Board.

Contents

Principal Investigator:	1
Funding Agency:	1
Protocol Summary	2
1. BACKGROUND AND RATIONALE	5
2. OBJECTIVES	6
2.1 Primary Objectives	6
2.2 Primary Outcomes	6
2.3 Secondary Outcomes	6
3. STUDY POPULATION	6
3.1 Target Population	6
3.2 Inclusion Criteria	6
4. STUDY DESIGN	7
4.1 Preliminary Studies	7
4.2 Overview	7
4.3 Study Duration and Timeline	10
4.4 Study Setting	10
5. STUDY PROCEDURES	11
5.1 Recruitment and Retention	11
5.2 Informed Consent	11
5.3 Compensation	12
5.4 Measures and Endpoints	13
5.5 Sources of Materials	14
6. STATISTICAL DESIGN AND POWER	14
6.1 Sample Size	14
6.2 Analysis Plan	14
6.2.1 Objective 1 Primary Analyses	14
6.2.2 Objective 1 Secondary Analyses	15
6.2.3 Objective 1 Exploratory Analyses	15
6.2.4 Objective 2 Analyses	15

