2.2 Primary Outcomes

Objective 1: Receipt of a molecularly-informed treatment recommendation for patients with metastatic NSq NSCLC at the time of the patient's initial oncology visit.

Objective 2: Individual and contextual factors (e.g., treatment knowledge, medical mistrust, clinical beliefs, organizational climate, patient-centered communication, financial toxicity, and knowledge of genetic testing) shaping trial effectiveness and patient experience.

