3.2 Inclusion Criteria

Objective 1:

Patients will be eligible for the randomized clinical trial if they:

- a) are aged 18 years or older
- b) based on cross-sectional imaging, are suspected to have locally advanced/metastatic NSCLC (as determined by the evaluating clinician)
- c) are scheduled for an appointment in the lung cancer evaluation clinic.

Objective 2:

Patients will be eligible if they were selected for participation in the pilot trial. Clinicians will be eligible if their area of expertise relates to the protocol topic (e.g., oncologists, nurses, clinical leads).

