6. STATISTICAL DESIGN AND POWER

6.1 Sample Size

Objective 1: Sample size is based on estimates of receiving a molecularly-informed treatment recommendation at the initial oncology visit. Based on our prior studies, we anticipate this will occur in 10% of patients in the usual care arm. This pilot study is designed to detect an absolute increase of 20% in our primary outcome for patients in the intervention arm. With a sample size of 124 participants and a two-sided alpha, we will have >80% power to detect an increase of this magnitude. Given the potential for drop-out of patients following randomization, we have increased the estimate by 10%, leading to a final sample size of 138 participants (69 in each arm). Although a difference <20% in our primary outcome rate may be clinically meaningful, this sample size is an optimal balance to allow an assessment of our primary and secondary outcomes and assess for mechanisms of action. Study outcomes will be used to preliminarily assess effectiveness across all outcome domains to inform the design of future studies, including a pragmatic trial, if warranted.

Objective 2: Proposed sample size is based on the estimated number of interviews needed to reach data saturation within each group and by intervention outcome to support mixed methods evaluation; however, interviews will continue until saturation is achieved.^{16,21}

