6.2 Analysis Plan

6.2.1 Objective 1 Primary Analyses

We will produce data summaries to assess data quality and demographic and clinical characteristics across arms. First, our primary analytic approach will be to conduct ITT analyses

using unadjusted logistic regression to compare the overall effectiveness of the intervention to result in receipt of a treatment recommendation at the initial in-person visit and time to treatment initiation. The ITT analysis provides an unbiased test of the overall effectiveness of the interventions. An additional analysis will adjust for imbalanced covariates, where imbalance is determined by standardized mean differences >0.1 . If the number of imbalanced covariates exceeds the number allowed for adjustment based on the number of events, we will prioritize covariates with the largest imbalances.

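### The primary test ignores suspected stage, which could be recorded before randomisation; adjusting for it would gain precision and guard against chance imbalance

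*Combined protocol and SAP*

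**What the plan says.** - **Allocation.** The Protocol Summary states "Eligible patients will be individually randomized to one of two arms", and 4.2 repeats that "eligible patients will be randomized to either enhanced synchronous telehealth nurse navigation or to usual care nurse navigation". Neither these nor 5.1 names a stratification factor, blocking or minimisation. Stratifying is mentioned only for the Objective 2 interview sample.
- **Eligibility.** Under 3.2, patients must be adults with a clinic appointment who, "based on cross-sectional imaging, are suspected to have locally advanced/metastatic NSCLC (as determined by the evaluating clinician"). The two stages form one combined category.
- **Primary outcome.** Section 2.2 defines it as "Receipt of a molecularly-informed treatment recommendation for patients with metastatic NSq NSCLC", at the initial oncology visit. Section 5.4 gives the same endpoint without the restriction to metastatic nonsquamous disease.
- **Primary analysis.** Section 6.2.1 specifies ITT, "using unadjusted logistic regression to compare the overall effectiveness of the intervention". An additional analysis adjusts for covariates whose standardised mean difference (SMD) exceeds 0.1, largest first if events are few. The candidate covariates are not listed.
- **Sample size.** Section 6.1: "we anticipate this will occur in 10% of patients in the usual care arm", with a 20-point absolute increase to be detected. "With a sample size of 124 participants and a two-sided alpha, we will have >80% power to detect an increase of this magnitude". This is raised to 138 (69 per arm) for drop-out.

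**The concern.** Eligibility mixes two groups, while 2.2 describes an outcome that belongs to one of them. If every randomised patient is in the denominator and the 2.2 wording applies, patients with suspected locally advanced disease should succeed less often, whichever arm they are in. Suspected stage is then a natural baseline predictor, and a clinician has to look at the imaging before the patient can be enrolled. The planned primary test makes no use of it.

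Two things are at stake. Variation that stage could explain stays in the error term. And with about 7 expected successes under usual care (0.10 × 69) and 21 under telehealth (0.30 × 69), a chance excess of suspected-metastatic patients in one arm moves the headline estimate. The SMD rule answers this only in part: it is supportive, is triggered by the data, and does not say that stage is among the covariates checked.

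**Working it through.** **1. The plan's own figures.** Inputs from 6.1: 10% v 30%, two-sided, power above 80%. The alpha level is not stated; 0.05 is assumed. With pooled variance and p̄ = 0.20:

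n per arm = [1.96·√(2·0.2·0.8) + 0.842·√(0.1·0.9 + 0.3·0.7)]² / 0.20² = (1.109 + 0.461)² / 0.04 = 61.6, so 62 per arm and 124 in total. Power at 62 per arm is 80.3%. Drop-out: 124 / 0.9 = 137.8, so 138. Both stated figures reproduce.

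**2. Assumptions the documents do not supply.** Let m be the share with suspected metastatic disease (0.5-0.7, that is 30-50% suspected locally advanced). Let r be the ratio of success in locally advanced to metastatic patients (0.1-0.5), taken as equal in both arms. Overall rates p stay at 10% and 30%, so success in metastatic patients is p / [m + r(1−m)]. For m = 0.5 and r = 0.1 the divisor is 0.55. That gives 18.2% and 54.5% in metastatic patients, and 1.8% and 5.5% in locally advanced patients.

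**3. Chance imbalance under simple randomisation.** The SD of the between-arm difference in the metastatic share is √(2m(1−m)/n). At 69 per arm this is 8.5 points for m = 0.5 and 7.8 for m = 0.7. A difference of at least 10 points means at least 7 patients. The exact binomial probability is 20% (m = 0.7) to 24% (m = 0.5) at 62 per arm, and 23% to 27% at 69 per arm. The chance that stage has an SMD above 0.1 is about 2[1 − Φ(0.1/√(2/69))] = 56%.

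**4. Shift in the estimate.** Each unit of imbalance moves the risk difference by the metastatic minus locally advanced success rate, averaged over the arms. For m = 0.5, r = 0.1: [(0.182 − 0.018) + (0.545 − 0.055)] / 2 = 0.327, or 3.3 points per 10 points of imbalance. For m = 0.7, r = 0.5: [(0.118 − 0.059) + (0.353 − 0.176)] / 2 = 0.118, or 1.2 points.

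**5. Power.** Simulation of 400,000 trials per setting with simple randomisation, comparing the unadjusted score test with a Mantel-Haenszel test stratified by suspected stage:

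| Locally advanced | r | 62 per arm: unadjusted → adjusted | 69 per arm: unadjusted → adjusted | Shift per 10 points |
|---|---|---|---|---|
| 50% | 0.1 | 81.0 → 87.9% | 85.6 → 91.0% | 3.3 |
| 50% | 0.25 | 81.0 → 84.8% | 85.6 → 88.3% | 2.4 |
| 50% | 0.5 | 81.1 → 82.4% | 85.6 → 86.2% | 1.3 |
| 30% | 0.1 | 81.1 → 84.5% | 85.7 → 88.2% | 2.5 |
| 30% | 0.25 | 81.1 → 83.5% | 85.7 → 87.1% | 1.9 |
| 30% | 0.5 | 81.0 → 82.0% | 85.7 → 86.1% | 1.2 |

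The gain runs from about 0.5 to 7 points. Stratifying the allocation as well changes the adjusted figure by under 1 point.

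**6. Unlucky trials.** In the 10-13% of trials where the telehealth arm has at least 10 points fewer metastatic patients, unadjusted power falls to about 58-80% across these settings. The adjusted test keeps 81-91%.

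**7. Type I error.** With no effect, both tests reject in about 5% of trials.

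**The case against.** The strongest reply is that nothing is broken. The sample size was computed for the unadjusted test at the overall rates, so variation due to stage is already inside the 80%. An unadjusted ITT test with an adjusted analysis in support is a legitimate choice. This stands: a reader might infer that the trial is underpowered or its estimate biased, and the documents support neither.

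A reader might also infer that stage is known at randomisation. Only a provisional suspicion is. Section 4.2 allows randomisation before the clinic visit and has staging imaging completed later, and 4.1 reports that in the sponsor's prior study stage was not yet established at biopsy. The limit is real but not fatal, because a baseline covariate need only predict the outcome. Misclassification raises r and shrinks the gain.

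It is equally tempting to say that stage decides who can reach the outcome. That rests on the wording in 2.2, which 5.4 does not repeat. Histology also matters and is not yet known. If only confirmed metastatic nonsquamous patients are analysed, most of the benefit goes.

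The shift is modest against a standard error of √(0.30/69) = 6.6 points, and the SMD analysis would often pick stage up if it were checked. Both points are fair, but neither protects the primary result.

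Finally, Figure 1 and one part of the document were not available, so stratification described only there cannot be excluded.

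**Conclusion.** The concern holds as a matter of efficiency and robustness. The figures of 124, 138 and power above 80% are right, and the unadjusted test is valid over repeated trials. What the plan forgoes is about 0.5 to 7 points of power (from 81% at 62 per arm or 86% at 69), and protection in the roughly 20-27% of trials with a stage imbalance of 10 points or more.

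These sizes rest on an assumed stage mix, an assumed success ratio, alpha of 0.05, and all randomised patients being in the denominator. With a weak predictor the gain is about a point or less. A reader might conclude that the missing stratified randomisation is the main fault. The calculation does not support that: nearly all of the gain comes from the analysis. The change is worth making because it costs little and does no material harm if stage proves uninformative.

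**What to change.** 1. In 4.2 and 5.1, record suspected stage (metastatic versus locally advanced) from the eligibility imaging before randomisation, and state in advance how indeterminate readings are classed. If enrolment has begun, abstract it from the pre-randomisation record by someone blind to arm.
2. In 6.2.1, prespecify suspected stage as a fixed term in the primary ITT analysis: a Mantel-Haenszel test, or logistic regression with a standardised risk difference. Keep the unadjusted result as supportive. About 28 expected events can carry one added term.
3. Reconcile 2.2, 5.4 and 6.2.1 on who is in the denominator and how patients with another diagnosis are counted, since the gain depends on it.
4. Stratified allocation by suspected stage is optional. No calculation here supports adding race as a stratum.

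The cost is one screening field and a sentence or two in 6.2.1, with no extra patients or procedures. The adjusted odds ratio becomes conditional on stage; reporting the standardised risk difference deals with that.

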4.3 Study Duration and Timeline

The study duration will be approximately 30 months. In months 1-3 we will conduct rapid-cycle approaches (RCAs) to optimize the telehealth navigation intervention.

Objective 1: In month 3, we will launch the study and randomize patients by study arm. The active trial enrollment period will be approximately 18 months in length to reach the estimated sample size of 138 patients. Longitudinal data capture to collect secondary outcome information for patients will be completed up to 1-year post-enrollment. Collection and verification of all study endpoints will be completed by 30 months after the study's start date.

Objective 2: Invitations for surveys and qualitative answers for patients will be sent within 6 weeks of the in-person oncology visit and will be completed within 3 months of invitation. Clinician and clinical leader interviews will be completed between months 15 and 21 of funding. Mixed methods analysis for Objective 2 will run from months 18-24.

An overview of the project timeline is below.

Table 1. Trial Timeline

Project Timeline	2023				2024				2025			
	Q1	Q2	Q3	Q4	Q1	Q2	Q3	Q4	Q1	Q2	Q3	Q4
Objective 1: Enroll eligible trial participants		•	•	•	•							
Objective 1: Deliver intervention		•	•	•	•							
Objective 1: Endpoint ascertainment & analysis		•	•	•	•	•	•					
Objective 2: Recruit & conduct patient interviews			•	•	•	•	•	•				
Objective 2: Recruit & conduct clinician interviews								•	•			
Objective 3: Mixed methods coding & analysis									•	•		
Submit manuscripts & disseminate results										•		

4.4 Study Setting

This study will occur within the University of Pennsylvania Health System (UPHS). Research activities will be conducted at the following UPHS sites:

- Hospital of the University of Pennsylvania Pavilion (HUP) – East
- Hospital of the University of Pennsylvania (HUP)
- Pennsylvania Hospital (PAH)
- Penn Presbyterian Medical Center (PPMC)

5. STUDY PROCEDURES

5.1 Recruitment and Retention

Objective 1: This study will employ a waiver of consent mechanism (see Section 5.2 Informed Consent). Eligible patients will be identified from weekly screening of appointments scheduled at the lung cancer evaluation clinic at Penn Medicine. The process will be optimized to identify all patients with suspected locally advanced/metastatic NSCLC. After eligibility is confirmed based on review of medical records, eligible participants will be randomized to receive an early enhanced synchronous telehealth nurse navigation visit (intervention) or standard nurse navigation (usual care). After completion of the initial clinical appointment, patients in the telehealth arm will be scheduled to receive a synchronous visit (with audio and video capabilities) with a lung cancer trained nurse navigator prior to their tissue biopsy.

Objective 2: This portion of the study will utilize prospective consent with waiver of written documentation (see Section 5.2 Informed Consent). An estimated 20-30 patients and 10-15 clinicians and clinical leaders will be interviewed (sample size dependent upon when data saturation is reached). Interview participants will also complete a survey before or at the time of the interview.

Patients: A sample of patients enrolled in the randomized clinical trial will be invited to participate in the semi-structured interview and survey via email or letter within 6 weeks of in-person visit. Participants will be invited in randomly selected batches (estimate approximately 5 per month to enhance capture over time) until we reach our target sample of approximately 20-30 patients. We will oversample for Black patients to understand effectiveness by race/ethnicity and stratify by trial outcome (treatment recommendation or not) and study arm (telehealth versus usual care) to understand factors contributing to both success and failure of the telehealth strategy (5-10 patients in each stratum).

Clinicians: Recruitment of clinicians will be similar to that of patients, except we will wait until the completion of the full trial to conduct interviews to avoid potential contamination. Clinicians will be randomly selected and invited via email. Recruitment will continue until we reach our target sample of 10-15 clinicians, purposively sampled by role (oncologists, nurses and advanced practice providers, practice managers, and health system leaders).

Interviews will be conducted by the qualitative data analyst and other trained research staff supervised by [name], a doctoral-trained qualitative researcher and Co-Investigator on the team. Interviews will be conducted in-person, by phone, or using a HIPAA-compliant video platform.

